### **Sample Size**

The sample size is at least 180 people for one-way analysis of variance with G \* Power version 3.1.19 software to determine a medium level (0.25) effect size between 4 groups at 0.80 power and 0.05 type I error level calculated (Tsai, 2016). Participants will be divided into 4 groups by randomization method.

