## **Randomization**

- ✓ Group I: The participants in the first group performed the surgical hand scrubbing for 1 minute and with using nail brush (n=45).
- ✓ Group II: The participants in the second group performed the surgical hand scrubbing for 1 minute and without using a nail brush (n=45).
- ✓ Group III: The participants in the third group performed the surgical hand scrubbing for 2 minute and with using nail brush (n=45).
- ✓ Group IV: The participants in the fourth group performed the surgical hand scrubbing for 2 minute and without using a nail brush (n=45).

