## **Statistical Analysis**

The data obtained from this study were evaluated by using the Statistical Package for the Social Sciences (SPSS, Inc., Chicago, IL, USA) 22.0 software program. After the data were transferred to the SPSS database, error controls were performed. Their compliance with a normal distribution was evaluated with Kolmogorov Smirnov test. The data determined were mean  $\pm$  standard deviation ( $X \pm SS$ ), median and minimum-maximum (min-max) for the variables determined by the measurement and number (n) and percent (%) for the variables determined by counting. Since the variables determined by counting did not comply with a normal distribution, the difference between the four groups was evaluated by the Chi square test. The one-way ANOVA test was used to investigate the difference between the four groups regarding the measured values for values complying with normal distribution and the Kruskal-Wallis test was used for the values that did not comply with a normal distribution. The Bonferroni correction was implemented to determine the source of the difference in group comparisons. In the comparison of four measurements within the group, the "Friedman Test" was used for data that did not conform to normal distribution. In order to understand from which measurement the difference arises, "Wilcoxon Test with Bonferroni Correction" was used as Post Hoc Test. The Mann-Whitney U test was used to investigate the difference between two groups of variables. A p value  $<0.05$  was accepted as statistically significant.

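### Both named post hoc steps use single-step Bonferroni; Holm, or Shaffer divisors behind the four-group test, would give more power per real pair at the same familywise error

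*Combined protocol and SAP*

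**What the plan says.** Randomization sets four arms of 45: brush or no brush, for 1 or 2 minutes. Sample Size powers only the overall comparison: "The sample size is at least 180 people for one-way analysis of variance", for "a medium level (0.25) effect size between 4 groups at 0.80 power and 0.05 type I error level calculated".

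In Statistical Analysis, "The one-way ANOVA test was used to investigate the difference between the four groups regarding the measured values" where these are normally distributed; Kruskal-Wallis is used otherwise. The follow-up is then given as "The Bonferroni correction was implemented to determine the source of the difference in group comparisons". Within each arm a Friedman test is followed by "Wilcoxon Test with Bonferroni Correction". A further sentence reads "The Mann-Whitney U test was used to investigate the difference between two groups of variables", and names no correction.

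The section mentions no stepwise or closed procedure and no simultaneous confidence intervals. It does not give the number of comparisons in either family. It does not say outright that the pairwise tests are run only after a significant four-group test, although the order of the text reads that way.

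**The concern.** The four-group test says only that some arm differs. The pairwise step says which scrub differs from which, and that is what a reader of the trial would act on. The trial is sized for the first question and not for the second, so power is short at the pairwise step.

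Single-step Bonferroni holds every pair to the strictest threshold even after some pairs have already been shown to differ. Holm relaxes the threshold as pairs are rejected and needs no extra assumption. Shaffer's method also uses the logic of pairwise equalities: once four means are known not to be all equal, several of the six equalities cannot hold together. The usual reason to keep single-step Bonferroni is that it gives simple simultaneous confidence intervals, and the plan reports none.

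**Working it through.** **Inputs.** From Sample Size: f = 0.25, four groups, alpha 0.05, power 0.80, N = 180. From Randomization: 45 per arm. Assumed, because the plan does not say: all six pairs are tested, data are normal with a common SD, there is no dropout, and pairwise tests use the pooled variance on 176 df.

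**1. The plan's own figure.** Noncentrality = N f² = 180 × 0.0625 = 11.25, with 3 and 176 df. Power is 0.804 at N = 180 and 0.794 at N = 176, so 180 is the smallest total with equal arms. The stated sample size reproduces.

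**2. Thresholds.** Four arms give 4 × 3 / 2 = 6 pairs. For the ordered p values, smallest first:

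| Step | Bonferroni | Holm | Shaffer, after a significant four-group test |
|---|---|---|---|
| 1 | 0.05/6 = 0.0083 | 0.05/6 = 0.0083 | 0.05/3 = 0.0167 |
| 2 | 0.0083 | 0.05/5 = 0.0100 | 0.0167 |
| 3 | 0.0083 | 0.05/4 = 0.0125 | 0.0167 |
| 4 | 0.0083 | 0.05/3 = 0.0167 | 0.0167 |
| 5 | 0.0083 | 0.05/2 = 0.0250 | 0.0250 |
| 6 | 0.0083 | 0.0500 | 0.0500 |

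Why 3: if the four means are not all equal, they split into groups of 3+1, 2+2, 2+1+1 or 1+1+1+1. These leave 3, 2, 1 or 0 true equalities, so at most three pairwise nulls can still be true. The all-equal case is covered by the four-group test at 0.05. The other cases are covered by 3 × 0.05/3 = 0.05.

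**3. Closed-form check on one pair.** In the two-versus-two pattern the arm means are ±0.25 SD, so a real pair differs by 0.5 SD. The standardised difference is 0.5 × √(45/2) = 2.372. By the normal approximation, power is Φ(2.372 − 2.638) = 0.395 at 0.05/6 and Φ(2.372 − 2.394) = 0.491 at 0.05/3.

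**4. Simulation.** There were 40,000 trials per pattern, each pattern with f = 0.25, and follow-up only if the F test was significant. Simulation error is at most √(0.25/40,000) = 0.0025.

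| Pattern and measure | Bonferroni | Holm | Shaffer |
|---|---|---|---|
| Two versus two: average power per real pair | 0.386 | 0.424 | 0.478 |
| Two versus two: all four real pairs found | 0.095 | 0.155 | 0.160 |
| One arm different: average power per real pair | 0.527 | 0.555 | 0.610 |
| All arms equal: familywise error | 0.039 | 0.039 | 0.049 |

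The gains per pair are 0.424 − 0.386 = 3.8 points (Holm) and 0.478 − 0.386 = 9.2 points (Shaffer) for two versus two. They are 0.555 − 0.527 = 2.8 and 0.610 − 0.527 = 8.3 points when one arm differs. Familywise error in these two partly-null patterns was at most 0.046. Neither Holm nor Shaffer lost a rejection that gated Bonferroni made.

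Holm was also checked, without the gate, in two further patterns: two extreme arms (0.281 to 0.304) and equally spaced arms (0.242 to 0.263). Its gain over all four patterns is therefore about 2 to 4 points.

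**5. Chance of naming at least one real pair.** Holm's first threshold equals Bonferroni's, so this chance is essentially unchanged: about 0.72 for both in two versus two, and about 0.77 for both when one arm differs. In two versus two the F test is significant in 0.803 of trials. Among those, Bonferroni names no differing pair in 10.2% and Shaffer in 2.3%, which gives 0.803 × 0.898 = 0.721 against 0.803 × 0.977 = 0.785. With one arm different, Shaffer raises the figure from 0.77 to 0.80.

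**The case against.** **Bonferroni is a valid choice.** That stands. It controls the familywise error, and a reader who infers that the plan's inference is wrong would be going beyond the text. The point is efficiency only.

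**Not every follow-up is Bonferroni-corrected.** Also right. A reader might infer that all follow-up comparisons are, but the Mann-Whitney sentence names no correction. Those tests may be the corrected post hoc tests or separate uncorrected ones; the text does not say.

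**Holm's gain is small, and dominance by Shaffer is conditional.** Both stand. Holm does nothing for the first rejection. Shaffer dominates Bonferroni run behind a significant four-group test. It cannot be said to dominate ungated Bonferroni: a related closed procedure behind the F test missed a pair that ungated Bonferroni found in 0.4% to 1.0% of simulated trials.

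**The hypotheses concern method and time, and the arms form a 2 × 2 layout.** If the two-versus-two split follows brush or duration, a direct comparison of 90 with 90 would have power 0.916, far above any pairwise figure here. That is a fair comment on the wider analysis. It does not remove the gain at the pairwise step that the plan does specify.

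**The within-arm tests compare time points, not arms.** Correct, so none of the power figures above apply to them. Their number is also unclear: Statistical Analysis speaks of four measurements and Data Collection of three stages. Holm's property of losing no rejection holds whatever the number.

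**The section is written in the past tense.** If p values had already been seen, moving to a more liberal adjustment is no longer a free edit and has to be disclosed.

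**Conclusion.** The point holds as a cheap improvement. Plain Bonferroni in the two named post hoc steps is valid but gives up power for no benefit that the plan uses. That Holm never rejects less is a theorem. The sizes are 2 to 4 points per real pair for Holm, with no gain in finding at least one. For Shaffer behind the four-group test they are about 8 to 9 points per pair in the two patterns examined; that figure should not be carried over to other patterns. Shaffer adds almost nothing over Holm for finding all four real pairs (0.160 against 0.155), because the two share the same threshold from the fourth step on.

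The sizes rest on six pairs, normal data, 45 per arm, no dropout and f = 0.25. The outcome is a colony count and may be analysed by ranks. That would shift the numbers but not Holm's advantage.

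A reader might also infer that real arm differences have been missed. The documents report no results and show no such thing; the statement is about power only.

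**What to change.** In Statistical Analysis:

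- State that the six between-arm comparisons are made only after a significant four-group test. Adjust them by Holm or, preferably, by Shaffer's divisors 3, 3, 3, 3, 2, 1 applied to the ordered unadjusted p values.
- Say whether the Mann-Whitney tests belong to this family of six or are separate and, if separate, what they compare and how they are adjusted.
- Use Holm for the within-arm Wilcoxon tests, and state how many time-point comparisons there are.
- If results had been seen before the change, label the re-analysis post hoc and report it beside the Bonferroni result.

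The cost is a sentence or two and ordering p values in a spreadsheet; no new data are needed. The one downside is that simultaneous confidence intervals matching a stepwise method are less simple than Bonferroni intervals. The plan reports none.

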## **Data Collection**

This research will take place in three stages. At all stages (before surgical hand scrubbing, immediately after and at the end of the surgery), culture will be taken from the active hands of the participants with the Glove Juice Method. At all stages, culture will be taken from the participants via Glove Juice Method.

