### *Glove Juice Method*

It is a method used to determine the number of bacteria on hand. In this method, individuals will be provided to wear gloves on their dominant hand. Powder-free sterile gloves were used for all sampling. Then, 50 ml of 'Tryptic Soy Broth' medium was placed inside the glove and all surfaces of the gloved hand were massaged for 60 seconds by the researcher. A sample was taken from the liquid in the glove using aseptic techniques and analyzed.

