### *Applications in Medical Microbiology Laboratory*

Before surgical hand scrubbing, samples taken with glove liquid technique were diluted 1:10 in Müller Hinton Broth broth in the laboratory (500  $\mu$ l sample, 4.5 ml. Müller Hinton Broth). And 300  $\mu$ l of it was placed on 5% sheep blood agar plates with sterile micropipettes. 1 ml each of the other samples (after surgical hand scrubbing and at the end of the surgery) was spread diluted into three 5 % sheep blood agar plates with sterile micropipettes. All samples were incubated at 35° C for 48 hours under atmospheric conditions. Total bacterial load was determined by counting the total colony forming units (CFU) on the plates.

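### Does the reference to four within-group measurements, when only three samples are taken, put the Friedman and Bonferroni-corrected Wilcoxon tests in doubt?

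*Combined protocol and SAP*

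**What the plan says.** Under Data Collection the plan states "This research will take place in three stages" and names them: "At all stages (before surgical hand scrubbing, immediately after and at the end of the surgery), culture will be taken". Under Applications in Medical Microbiology Laboratory the same three specimens appear, with one handling rule for the first ("Before surgical hand scrubbing, samples taken with glove liquid technique were diluted 1:10") and another for the remaining two ("1 ml each of the other samples (after surgical hand scrubbing and at the end of the surgery"). The Glove Juice Method section limits sampling to one hand: "individuals will be provided to wear gloves on their dominant hand".

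The Statistical Analysis section then introduces the Friedman test with the words "In the comparison of four measurements within the group". It follows this with a Wilcoxon test under Bonferroni correction to locate any difference. It gives no number of pairs, divisor or adjusted threshold, only the general 0.05 significance level.

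**The concern.** The number of repeated measurements fixes two features of this analysis: the degrees of freedom of the Friedman test and the number of pairwise Wilcoxon tests sharing the Bonferroni correction. If the analysis section counts four and the design supplies three, a reader cannot take the divisor from the analysis section alone. A pairwise p-value of 0.012 would be significant with a divisor of three and not with a divisor of six.

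Two things could be at stake. If the divisor for four measurements were applied to the three pairs that exist, the within-group comparisons would lose power for no benefit. If four were the true count, a sampling stage would be missing from the description of data collection.

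**Working it through.** **The plan's own figure.** The only computed figure in the document is the sample size: four groups, effect size f = 0.25, power 0.80, type I error 0.05 (Sample Size section). For one-way ANOVA the noncentrality is f² × N, with 3 and N − 4 degrees of freedom.

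- The smallest total N reaching 0.80 is 179 (power 0.8015).
- Balanced over four groups this becomes 180, or 45 per group: noncentrality 0.0625 × 180 = 11.25, power 0.804.
- At 176 the power is 0.794.

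The figure of 180 therefore reproduces. It rests on the between-group comparison alone, so the number of repeated measurements does not enter it.

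**Looking for a fourth measurement.**

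| Possible source | What the document says | Fourth measurement? |
|---|---|---|
| Another sampling time | Data Collection lists three times; the laboratory section processes the same three | No |
| The other hand | Glove Juice Method samples the dominant hand only | No |
| The three agar plates | Platings of a single specimen | No |
| The four groups | Separate sets of participants, so not repeated measures within a group | No |

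The only other four in the design is the number of groups, which the Statistical Analysis section also mentions in the sentences on the between-group tests. Carry-over of that number is a plausible origin, though the document does not confirm it.

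**What each count implies.** With k measurements, Friedman has k − 1 degrees of freedom and there are k(k − 1)/2 pairs.

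| k | Friedman df | 5% critical value | Pairs | Bonferroni threshold |
|---|---|---|---|---|
| 3 | 2 | 5.99 | 3 | 0.05/3 = 0.0167 |
| 4 | 3 | 7.81 | 6 | 0.05/6 = 0.0083 |

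**What the analyst would do.** The data hold three values per participant. The Friedman test takes its degrees of freedom from the measurements supplied, so it has 2. Three pairs can be formed, and a Bonferroni correction over them divides by three. The k = 4 row cannot be carried out on the samples described.

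**The worst case.** Suppose the analyst formed three pairs and still divided by six. The family-wise bound would be 3 × 0.05/6 = 0.025 instead of 0.05, so type I error is not inflated. The plan gives no within-group effect or power, so any loss of power has to be assumed. The two-sided critical values are 2.394 at 0.0167 and 2.638 at 0.0083. By the normal approximation, power at the stricter threshold is Φ(2.394 + z − 2.638), where z is the normal quantile of the power at 0.0167. Assumed powers of 70%, 80% and 90% would become about 61%, 72% and 85%. These figures measure a supposed mistake that nothing in the document suggests; they do not measure a defect in the plan.

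**The case for a change.** The strongest case for acting is that the document contradicts itself on a count that determines a significance threshold, that no innocent reading removes the contradiction, and that only the sponsor can say which count is right. The within-group Wilcoxon tests are the plan's stated means of finding which measurement differs, and correcting one sentence costs almost nothing. The family is also open in another respect: if the correction spanned all four groups, the divisor would be 4 × 3 = 12 (0.05/12 = 0.0042) for three measurements, or 4 × 6 = 24 (0.05/24 = 0.0021) for four.

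The contradiction stands; its consequence does not. The divisor need not come from the analysis section, because Data Collection gives the count and names each sample, and the laboratory section agrees. Two detailed and concordant sections outweigh one word. The plan states no divisor or threshold that is wrong, so writing in 0.0167 would only spell out what the named correction already means for three pairs. Whether to pool over groups is a separate choice that the word four neither creates nor settles; since the comparison is described as within the group, correcting within each group is the natural reading. A missing sampling stage would matter more, but no section supports one.

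**Conclusion.** This is a clerical slip with no effect on the results. Following the plan on the three samples it describes gives Friedman on 2 degrees of freedom and three Wilcoxon pairs per group, each at 0.0167 if each group is its own family. Even the unlikely misuse of a divisor of six would err on the strict side, with a family-wise bound of 0.025. Both stated hypotheses concern differences between scrubbing methods and between durations. They are tested between groups, so neither they nor the sample size of 180 depend on this count.

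The conclusion assumes that the three samples in Data Collection and in the laboratory section are all that were taken, which is what both sections say. Replacing the word four with three would be a tidy editorial correction, but it would alter no analysis, threshold or conclusion.

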### **Hypothesis**

#### 1. Method

H0: There is no difference between the effectiveness of different surgical hand scrubbing methods on the bacterial flora in the hand

H1: There is a difference between the effectiveness of different surgical hand scrubbing methods on the bacterial flora in the hand.

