#### 2. Time

H0: There is no difference between the effectiveness of different the duration of scrubbing time on the bacterial flora in the hand.

H1: There is a difference between the effectiveness of different the duration of scrubbing time on the bacterial flora in the hand.

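### Across the sampling stages the plan names only within-arm tests, which cannot test its between-arm hypotheses; no arm-by-stage or baseline-adjusted comparison is specified

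*Combined protocol and SAP*

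**What the plan says.** Both hypotheses concern differences between arms. The method hypothesis reads "There is a difference between the effectiveness of different surgical hand scrubbing methods on the bacterial flora in the hand" and the time hypothesis reads "There is a difference between the effectiveness of different the duration of scrubbing time on the bacterial flora in the hand".

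Data Collection sets three sampling points per participant: "At all stages (before surgical hand scrubbing, immediately after and at the end of the surgery), culture will be taken".

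Statistical Analysis contains two kinds of test on the counts:

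- **Between arms.** One-way ANOVA if normal, Kruskal-Wallis if not, across the four groups, with a Bonferroni correction to locate differences. Mann-Whitney is named for two-group comparisons. The section does not say whether the value analysed is pre-scrub, post-scrub, end of surgery or a change between them.
- **Across stages.** "In the comparison of four measurements within the group", a Friedman test is used for non-normal data. "In order to understand from which measurement the difference arises", it is followed by Wilcoxon tests with Bonferroni correction. No repeated-measures method is named for normal data.

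Sample Size rests on the between-arm test: "The sample size is at least 180 people for one-way analysis of variance".

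**The concern.** A within-arm test asks whether counts in that arm changed. The hypotheses ask whether arms differ. A significant change in one arm beside a non-significant change in another is not evidence of a difference between them, because the two results can part by chance when the true changes are equal.

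The gap matters most for the third sample. Whether a method or duration keeps counts low through the operation is a natural reason to sample at the end of surgery. The plan names no between-arm analysis that uses a participant's stages together. A reader of the results who wants to know about change between stages is given only four separate sets of within-arm p values, which the plan does not label descriptive. Setting them side by side has no error control.

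The drop from before to just after the scrub may well be significant in every arm. In that case the within-arm tests are uninformative about the arms rather than misleading.

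**Working it through.** **1. The plan's own figure.** Inputs from Sample Size: "to determine a medium level (0.25) effect size between 4 groups at 0.80 power and 0.05 type I error level calculated". For one-way ANOVA with N = 180, df = 3 and 176, noncentrality N × f² = 180 × 0.0625 = 11.25. Power is 0.804. The smallest N reaching 0.80 is 179, or 180 with equal arms. The stated 180 (45 per arm) is reproduced, and it belongs to the between-arm test.

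**2. Chance that arms with identical true change disagree.** Inputs: n = 45 per arm (Randomization); three stages (Data Collection), hence three pairs and alpha = 0.05/3 = 0.0167, two-sided. The standardised paired change dz (mean change divided by the SD of the within-person difference) is *assumed*, because the documents give neither a mean change nor an SD.

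Power per arm, p, comes from the noncentral t with 44 df and noncentrality dz × √45. The four arms are independent, so

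P(at least one significant and at least one not) = 1 − p⁴ − (1 − p)⁴.

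| dz | p | p⁴ | (1 − p)⁴ | Disagreement |
|---|---|---|---|---|
| 0.3 | 0.33 | 0.01 | 0.20 | 78% |
| 0.4 | 0.58 | 0.11 | 0.03 | 86% |
| 0.5 | 0.80 | 0.41 | 0.00 | 58% |
| 0.6 | 0.93 | 0.76 | 0.00 | 24% |
| 0.7 | 0.98 | 0.94 | 0.00 | 6% |
| 0.8 | 0.997 | 0.99 | 0.00 | 1% |

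At dz = 1.0 the figure is below 0.1%.

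**3. Simulation check.** 2,000 trials per setting, 45 per arm, normal data, within-person correlation 0.5, end-of-surgery change set at half the immediate change, all arms identical:

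| dz | Wilcoxon at 0.05/3, disagreement | Friedman at 0.05, disagreement |
|---|---|---|
| 0.3 | 77% | 73% |
| 0.4 | 87% | 88% |
| 0.5 | 62% | 75% |
| 0.6 | 29% | 49% |
| 0.8 | 2% | 7% |
| 1.0 | 0.2% | 0.3% |

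Across all settings run (dz 0 to 2), a direct Kruskal-Wallis test of the before-to-after change between arms rejected in 4.5% to 5.8% of trials, and Kruskal-Wallis on the post-scrub value in 4.4% to 5.9%. Both hold the nominal 5%.

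**4. Three stages or four measurements.** If four measurements were meant, there are six pairs and alpha = 0.05/6. Disagreement at dz 0.3, 0.4, 0.5 and 0.6 becomes 66%, 87%, 73% and 37%. The conclusion is the same, but the threshold depends on which count is right.

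**5. Level and change answer different questions.** Two simulated cases, with assumed values, show it in each direction:

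- Arms differ by 0.5 SD just after the scrub and then rise by the same amount (correlation 0.5). Kruskal-Wallis on the end-of-surgery value rejects in 78% of trials; on the change from post-scrub, in 5%.
- Two arms are 0.5 SD lower just after the scrub and all arms end at the same level (no within-person correlation). The test of change rejects in 50%; the test of the end-of-surgery value, in 4%.

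Neither quantity can stand in for the other. The second case also shows that a larger rise can simply reflect a better scrub.

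**The case against.** The strongest reply is that the plan already has a between-arm test. The four-group ANOVA or Kruskal-Wallis is the test the trial was sized on, and after randomisation a comparison of post-scrub or end-of-surgery counts is a valid test of both hypotheses, which speak of effectiveness and not of change scores. This stands. A reader might infer that the hypotheses are left to the within-arm tests alone; the documents do not support that.

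Nor do they say that within-arm significance will be compared across arms or used to decide a hypothesis. Friedman tests reported beside between-arm tests are not an error in themselves. The harm is a reading that the plan leaves open, not one that it prescribes.

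A third reply is that frequent disagreement depends on the chosen range of dz. This also stands. Frequent disagreement needs a small to moderate change. Such a change is plausible from post-scrub to end of surgery, but the documents do not establish it, and a large fall after antiseptic would make every arm significant.

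Finally, change from post-scrub to end of surgery starts from a value that the scrub has already altered, so it cannot serve alone as the test of a maintained effect. This is correct and shapes the fix.

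These replies do not supply a between-arm analysis across stages. The quantity entering the ANOVA is unspecified, no baseline adjustment is named, and the within-arm tests carry no stated role.

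**Conclusion.** The point holds in a limited form. The plan can validly compare levels between arms at a stage, once the stage is named. It names no between-arm analysis across stages, and the within-arm Friedman and Wilcoxon p values cannot fill that place.

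If they were read as if they could, arms with identical true change would disagree on significance in 24% to 86% of trials for dz of 0.3 to 0.6 (45 per arm, alpha 0.05/3). At dz of 0.8 or above the calculation gives about 1% or less, with simulation at 0.8 giving 2% for Wilcoxon and 7% for Friedman; the tests are then nearly always significant everywhere and silent on arm differences. These figures rest on an assumed dz, three stages and independent arms. It would go too far to say that misleading disagreement is likely in this trial, because nothing in the documents fixes dz.

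This is a worthwhile, inexpensive improvement to the analysis, not a defect that leaves the trial without a valid test.

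**What to change.** 1. Make one between-arm longitudinal model the analysis of the hypotheses: log10 CFU per hand at post-scrub and end of surgery, with arm, stage, arm × stage, a participant random effect and the pre-scrub log count as baseline. Counts must first be put on a common per-hand scale, since the laboratory section plates pre-scrub and later samples at different dilutions and volumes.
2. Take the tests of the two hypotheses from that model as arm contrasts: brush against no brush, and one duration against the other, each at post-scrub and at end of surgery. State in advance which stage is primary or how multiplicity is handled.
3. Report the arm difference in change from post-scrub to end of surgery as secondary, always beside the end-of-surgery level, because the post-scrub value is already affected by the intervention.
4. Label the within-arm Friedman and Wilcoxon results descriptive, and state that no conclusion about the arms rests on their p values.
5. If the four-group ANOVA or Kruskal-Wallis is kept, name the stage and quantity it uses.
6. Reconcile the four measurements in Statistical Analysis with the three stages in Data Collection.

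The cost is analysis wording and one model on data the trial already collects; no further participants or samples are needed. The downside is reliance on a log scale and a rule for zero counts, to be fixed before the data are analysed, with a rank-based sensitivity analysis if zeros are common.

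### No post-scrub stage is named as deciding, so the four-group test can be significant at either of two stages and the 0.05 type I error behind the sample size does not hold

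*Combined protocol and SAP*

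**What the plan says.** The Sample Size section bases the trial on one test: "The sample size is at least 180 people for one-way analysis of variance", for a "medium level (0.25) effect size" across four groups, "at 0.80 power and 0.05 type I error level calculated". The Randomization section gives 45 participants per group.

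The Hypothesis section sets out two numbered hypotheses, method and time, each with its own H0 and H1. Both concern bacterial flora on the hand, and neither mentions a time point.

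Data Collection then sets three cultures per participant: "At all stages (before surgical hand scrubbing, immediately after and at the end of the surgery), culture will be taken". Two of these follow the scrub. No section names a primary outcome or a primary stage.

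Statistical Analysis compares the four groups by one-way ANOVA or, for non-normal data, Kruskal-Wallis. Bonferroni appears twice: to locate the source of a difference between groups, and for Wilcoxon tests between measurements within a group. A Mann-Whitney test is listed without being tied to a hypothesis, a stage or a correction. The section closes with one general threshold: a p value below 0.05 "was accepted as statistically significant".

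**The concern.** The 0.05 in the sample size belongs to one test. The analysis section lets that test be run at both post-scrub stages, each judged at 0.05, and nothing says which result settles the hypotheses. A difference immediately after scrubbing, at the end of surgery, or at both could be reported as support for H1. The chance of a false positive conclusion is then larger than the figure on which the trial was sized. A reader of the results could not tell whether the stage put forward was chosen in advance or because it was the one that reached significance.

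**Working it through.** **Inputs.** From Sample Size: f = 0.25, four groups, power 0.80, "0.05 type I error level", N = 180. From Randomization: 45 per group. From Data Collection: two post-scrub stages. From Statistical Analysis: threshold 0.05 and no correction across stages. The correlation between the two stages is not in the documents and is varied from 0 to 0.9 as an assumption.

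**Step 1: the plan's own figure.** Power of a one-way ANOVA comes from the noncentral F distribution with 3 and N−4 degrees of freedom and noncentrality N × f².
- N = 180: noncentrality 180 × 0.0625 = 11.25, power 0.804.
- N = 176: noncentrality 11.0, power 0.794.

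With equal groups, 180 is therefore the smallest total that reaches 0.80. The stated figure reproduces, and its 0.05 covers exactly one four-group test.

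**Step 2: the same test at two stages.** If the stages were independent, the chance of at least one p<0.05 under no true effect would be 1 − 0.95² = 0.0975. The upper bound is 0.05 + 0.05 = 0.10. For correlated stages, 40,000 null trials per setting were simulated (4 × 45, normal data). The last column belongs to step 3.

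| Assumed correlation between stages | One four-group test per stage (2 tests) | Method and time tested separately per stage (4 tests) |
|---|---|---|
| 0 | 0.096 | 0.185 |
| 0.3 | 0.093 | 0.179 |
| 0.5 | 0.090 | 0.170 |
| 0.7 | 0.083 | 0.159 |
| 0.9 | 0.071 | 0.137 |

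For the planned four-group test the range is about 0.07 to 0.10. It falls back to 0.05 only if the two stages are perfectly correlated. The independence figure and the upper bound apply equally to Kruskal-Wallis, provided each such test holds its own 0.05.

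**Step 3: a different reading.** If method and time were each tested as separate main effects at both stages, there would be four tests. Independence would give 1 − 0.95⁴ = 0.185, and the simulated values are in the last column. Statistical Analysis does not specify such tests.

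**Step 4: what a correction does.**
- One primary stage, tested at 0.05: error 0.05, power 0.804 at N = 180, as planned.
- Both stages eligible, each at 0.05/2 = 0.025: error at most 0.05 (1 − 0.975² = 0.049 if independent). Power of the four-group test at a given stage is 0.716 at N = 180; N = 212 would restore 0.80.

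**Step 5: power for separate main effects.** With 1 and 176 degrees of freedom and f = 0.25 for each main effect, power is 0.916 at 0.05 and 0.862 at 0.025. The plan, however, gives 0.25 as the "effect size between 4 groups at 0.80 power". If that four-group effect were split equally between method and time with no interaction, each would have f = 0.25/√2 = 0.177, and power would be about 0.65 at 0.05 and 0.55 at 0.025.

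**The case against.** The plan is not silent on multiplicity: Bonferroni is applied to pairwise follow-up in both places where the plan describes it. It can also be said that the freedom to claim success at either stage is inferred from what the plan leaves out, and that this is a gap in specification rather than a wrong rule. Both observations are fair. Neither removes the point, because the only stated threshold is 0.05 and no correction reaches across stages.

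Three stronger readings are tempting, and the documents do not support them.

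- **A false-positive chance near 0.19.** A reader might multiply two hypotheses by two stages. That requires separate tests of method and time, whereas the stated comparison is one four-group test. The Mann-Whitney sentence leaves the possibility open but is attached to no hypothesis or stage.
- **Compulsory adjustment across method and time.** These are separately numbered hypotheses about different factors. Testing each at 0.05 is a defensible choice if declared, so adjustment is optional. The stage problem remains within each hypothesis.
- **Error control at almost no cost in power.** The claim that main-effect power stays above 0.80 needs f = 0.25 for each factor, which the plan does not state.

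The choice of stage is not clear-cut either. The aim of preventing surgical site infection could favour the end of surgery. The section on volunteers' exclusion ends data collection after a glove breach but does not say whether samples already taken are kept. If they are dropped, the immediate post-scrub data are selected by the same events.

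Finally, Study Setting and Statistical Analysis are partly in the past tense, and the latter reports that some variables were not normally distributed. The data may already have been examined, and a stage named afterwards does not restore error control by itself.

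**Conclusion.** The point holds for the four-group test that the plan specifies. Followed as written, the plan gives a chance of about 0.07 to 0.10 of a significant four-group result at one or both post-scrub stages when nothing differs, against the 0.05 used for sizing. This rests on an assumed between-stage correlation of 0.9 to 0 and on 45 per group. The figure would be about 0.14 to 0.19 only if method and time were tested separately at each stage. The sample size of 180 is not an arithmetic error; what is missing is a statement of where its single test is to be made. It should be corrected, because it determines what counts as a positive trial.

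**What to change.** In Sample Size and Statistical Analysis, name one post-scrub stage as primary and test H1 at that stage at 0.05. Immediately after scrubbing is a reasonable choice: it measures the scrub itself, and it includes participants whose gloves are later breached, provided their sample is kept. The plan should say whether it is. Report the other stage as secondary, with estimates and confidence intervals, and state that it cannot support H1 on its own.

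This takes a few sentences and no extra participants; the planned test keeps its 0.05 and its power of 0.804 at N = 180. The price is that a significant result at the secondary stage alone no longer supports H1.

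If the stage was not fixed before the data were seen, say that the choice is post hoc, report both stages, and require p<0.025 at a stage for a claim based on it. Power at each stage is then 0.716 with 180 participants.

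State whether method and time are treated as separate questions, each at 0.05, or adjusted jointly; either is acceptable if declared. Do not claim main-effect power above 0.80 unless the plan states that f = 0.25 applies to each main effect.
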